7.2.5 Reporting Exposure to Talimogene Laherparepvec

If a household member, caregiver, or healthcare provider who have had close contact with the subject is suspected to have been exposed to talimogene laherparepvec (eg, have or who have had signs or symptoms suspected to be herpetic in origin or accidentally exposed to talimogene laherparepvec), report the potential or known unintended exposure to talimogene laherparepvec, suspected related signs or symptoms, and detection of talimogene laherparepvec in a subject's household member, caregiver, or healthcare provider as specified [Section 9.4](#).

7.2.6 Optional Photography Substudy (Select Sites Only)

For sites selected to participate in the photography substudy, photographs of **all** visible (ie, visible protrusion from skin surface) cutaneous and subcutaneous tumor lesions will be performed as detailed in [Section 7.2.2](#) until end of treatment (**always within 3 days prior to investigational product administration**). Amgen may use, copy, and/or distribute the photographs for educational purposes, in scientific lectures, journal articles, and textbooks. Amgen may also use the photographs for general commercial purposes and may have the photographs published, circulated or presented in any way either alone or with other written, printed, graphic, or audio matter to members of the medical, nursing, pharmaceutical and related professions, as well as to the public at large. The subjects' identity will not be disclosed in any photographs. Amgen would only show the photographs of subjects from the neck down excluding face or scalp without identifying the subject facial characteristics. Any tattoos or other body marks that may identify the subjects will be covered. Amgen may edit, reduce, enlarge or otherwise change the photographs. The photographs may have commercial value to Amgen. Neither Amgen nor the investigator will compensate the subject for the photographs or the use of the photographs. Refer to the Photography Manual for further instructions.

7.3 Biomarker Development

Biomarkers are objectively measured and evaluated indicators of normal biologic processes, pathogenic processes, or pharmacologic responses to a therapeutic

intervention. In oncology, there is particular interest in the molecular changes underlying the oncogenic processes that may identify cancer subtypes, stage of disease, assess the amount of tumor growth, or predict disease progression, metastasis, and responses to investigational product.

Amgen may attempt to develop test(s) designed to identify subjects most likely to respond positively or negatively to talimogene laherparepvec.

7.3.1 Blood Samples

Blood samples are to be collected for biomarker development at time points designated in the Schedule of Assessments (Table 2) and as described in Section 7.2.2

Blood samples (both cells and plasma) will be analyzed for changes in the immune system before and during treatment that correlate with clinical response. Tumor antigen specific cytotoxic T cells will be enumerated in blood samples CCI [REDACTED]

Changes in circulating immune cells will be characterized by flow cytometry to enumerate the number of immune cell subsets CCI [REDACTED]

T cell subsets will also be characterized for activation markers CCI [REDACTED]

Refer to the Laboratory Manual for detailed collection and handling procedures for blood samples for biomarker development.

7.3.2 Tumor Tissue Samples

Archived Tumor Tissue Sample:

A block of formalin-fixed paraffin-embedded tumor tissue (**from the current diagnosis**) collected prior to the study is to be sent to the central laboratory along with the corresponding pathology report as described in the Schedule of Assessments (Table 2) and in Section 7.2.2.

The tumor block is to be carefully selected by a pathologist or a skilled experienced histology associate to include generous tumor tissue using the Pathology Report as a guide. In the event that multiple tumor blocks with generous tumor tissue are available, the most recent block should be submitted. In lieu of a block, approximately 20 unstained sections on charged slides from the same block can be submitted.

Analyses of tumor specific mutations or epigenetic changes may be performed (eg somatic mutations) on tumor tissues.

Refer to Laboratory Manual for specific instructions on tumor block/slide preparation.

Tumor Biopsy Samples:

On study biopsies will be collected, as described in the Schedule of Assessments (Table 2) and in Section 7.2.2, to characterize the mechanism of systemic action of talimogene laherparepvec. Collecting a biopsy from an uninjected lesion during the treatment period (eg, **within 7 days prior to dosing** at week 6) is critical for identifying the changes in intratumoral CD8+ cell density that occur following talimogene laherparepvec treatment and that may be associated with clinical benefit. Refer to the Laboratory Manual for specific instructions on tumor biopsy procedures.

CD8⁺ cell density will be determined in tumor tissue samples by CD8 specific immunohistochemistry. The tissue samples will be analyzed by immunohistochemistry blinded to study outcomes at a central laboratory. The entire tissue slide will be stained and scanned to create a digital image. Image analysis software will be used to exclude areas of adjacent normal tissue, necrotic tissue and large blood vessels and to define the region of interest which will be measured in mm². Within the region of interest, the image analysis software will measure the number of CD8⁺ T cells and report the number of CD8⁺ T cells per square millimeter (eg, #CD8+ cells/mm²).

In addition to CD8 cells, a variety of other tumor infiltrating immune cell markers may be explored by immunohistochemistry CCI

The tumor samples will also be analyzed for mutations or other changes within the tumor that make it more resistant to talimogene laherparepvec viral replication.

7.4 Pharmacogenetic Studies

If the subject consents to the optional pharmacogenetic portion of this study, DNA analyses on blood samples may be performed. These optional pharmacogenetic analyses focus on inherited genetic variations to evaluate their possible correlation to the disease and/or responsiveness to the therapies used in this study. The goals of the optional studies include the use of genetic markers to help in the investigation of cancer and/or to identify subjects who may have positive or negative response to talimogene laherparepvec. No additional samples are collected for this part of the study. For subjects who consent to this/these analysis/analyses, DNA may be extracted.

7.5 Sample Storage and Destruction

Any blood or tumor samples collected according to the Schedule of Assessments (Table 2) can be analyzed for any of the tests outlined in the protocol and for any tests necessary to minimize risks to study subjects. This includes testing to ensure analytical methods produce reliable and valid data throughout the course of the study. This can also include, but is not limited to, investigation of unexpected results, incurred sample reanalysis, and analyses for method transfer and comparability.

All samples and associated results will be coded prior to being shipped from the site for analysis or storage. Samples will be tracked using a unique identifier that is assigned to the samples for the study. Results are stored in a secure database to ensure confidentiality.

If informed consent is provided by the subject, Amgen can do additional testing on remaining samples (ie, residual and back-up) to investigate and better understand the cancer, the dose response and/or prediction of response to talimogene laherparepvec, characterize antibody response, and characterize aspects of the molecule (eg, mechanism of action/target, metabolites). Results from this analysis are to be documented and maintained, but are not necessarily reported as part of this study. Samples can be retained for up to 20 years.

Since the evaluations are not expected to be available in time to benefit the subject directly or to alter the treatment course, the results of qPCR testing from swabs of cold sores, vesicles, and other lesions suspected to be herpetic in origin will not be provided unless requested by the investigator or the subject. Results may not be available until the end of the study. Results of biomarker development or other exploratory studies are not placed in the subject's medical record and are not to be made available to the subject, members of the family, the personal physician, or other third parties, except as specified in the informed consent.

The subject retains the right to request that the sample material be destroyed by contacting the investigator. Following the request from the subject, the investigator is to provide the sponsor with the required study and subject number so that any remaining blood or tumor samples and any other components from the cells can be located and destroyed. Samples will be destroyed once all protocol-defined procedures are completed. However, information collected from samples prior to the request for destruction, will be retained by Amgen.

The sponsor is the exclusive owner of any data, discoveries, or derivative materials from the sample materials and is responsible for the destruction of the sample(s) at the request of the subject through the investigator, at the end of the storage period, or as appropriate (eg, the scientific rationale for experimentation with a certain sample type no longer justifies keeping the sample). If a commercial product is developed from this research project, the sponsor owns the commercial product. The subject has no commercial rights to such product and has no commercial rights to the data, information, discoveries, or derivative materials gained or produced from the sample.

See [Section 11.3](#) for subject confidentiality.

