10.3.2 Primary Analysis

The clinical study report (CSR) will be written based on the results of the primary analysis. The main goals of the primary analysis are to evaluate the ORR and correlation of baseline intratumoral CD8+ cell density and the likelihood of response to talimogene laherparepvec, in addition to the correlation between changes in intratumoral CD8+ cell density during treatment and objective response. The timing of the primary analysis will be when all subjects have had the opportunity to complete 12 months of treatment of talimogene laherparepvec.

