Appendix A. Conventions for Clinical Data That Require Imputation for Partial or Missing Date.....	23
Appendix B. Wilson's Score Method with Continuity Correction in Calculating the 95% Confidence Intervals for Difference in 2 Independent Proportions	25

Table of Abbreviations

Abbreviation/Acronym	Definition
AE	Adverse event
CI	Confidence interval
CR	Complete response
CRF	Case report form
CT	Computerized Tomography
CTC	Common Toxicity Criteria
CTCAE	Common Toxicity Criteria for Adverse Events
DMP	Data management plan
DOR	Duration of Response
DRR	Durable Response Rate
DTP	Data transfer plan
ECOG	Eastern Cooperative Oncology Group
eCRF	Electronic Case Report Form
EOI	Event of Interest
HR	Hazard ratio
HSV	Herpes simplex virus
HSV-1	Herpes simplex virus type 1
IP	Investigational product
IPD	Important protocol deviation
IVRS	Interactive Voice Response System
KM	Kaplan-Meier
MedDRA	Medical Dictionary for Regulatory Activities
ND	Not done
NPV	negative predictive value
OR	Objective response (CR or PR)
ORR	Objective response rate
PD	Progressive disease
PFU	Plaque-forming unit
PPV	positive predictive value
PR	Partial response
PT	Preferred term
qPCR	Real-time polymerase chain reaction
SAE	Serious adverse event
SAP	Statistical analysis plan

Abbreviation/Acronym	Definition
SD	Stable disease
SMQ	Standardized MedDRA Queries
SOC	System organ class
SOP	Standard Operating Procedure
TTF	time to treatment failure
UE	Unevaluable for tumor response
ULN	Upper limit of normal
WHO	World Health Organization
WHODRUG	World Health Organization Drug Dictionary

1. Introduction

The purpose of this statistical analysis plan (SAP) is to provide details of the statistical analyses that have been outlined within the protocol 20120325 entitled “A Phase 2, Multicenter, Open-label, Single-arm Trial to Evaluate the Correlation Between Objective Response Rate and Baseline Intratumoral CD8+ Cell Density in Subjects With Unresected Stage IIIB to IVM1c Melanoma Treated with Talimogene Laherparepvec”.

The scope of this plan includes the primary analysis that is planned and will be executed by the Biostatistics department at Amgen unless otherwise specified. A separate SSAP will be prepared for the exploratory objectives and these analysis may be reported separately.

2. Objectives

Primary Objective:

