Deaths of all causes that occur any time during the study are defined as on-study deaths. This may include deaths that occur beyond the end of the treatment period. Note that this study has a long-term survival follow-up after the safety follow-up, deaths that occur after the study long-term survival follow-up will be reported in study, 20120139, which is the registry study for long-term follow up of clinical trial subjects who have completed talimogene laherparepvec treatment.

7. Analysis Subsets

Safety Analysis Set: The safety analysis set will include all subjects who have received at least 1 dose of talimogene laherparepvec. The efficacy analysis and safety analysis will be performed on the safety analysis set.

CCI

Reactive Swab Analysis Set

Subjects who are enrolled, receive at least one dose of talimogene laherparepvec, and have at least one swab sample collected from lesions that are suspected to be herpetic

in origin. This analysis set is used to examine the number of subjects with a lesion suspected to be herpetic, and detection of talimogene laherparepvec DNA by qPCR in lesions suspected to be herpetic in origin.

8. Covariates and Subgroups

The following covariates may be used to examine efficacy and safety in subgroups or in multivariate analyses:

- Region, if applicable (by countries)
- Age at baseline: < 50, ≥ 50; < 65, ≥ 65; < 75, ≥ 75 years
- Disease stage at baseline: IIIB and IIIC vs IVM1a vs IVM1b vs IVM1c
- Baseline LDH ≤ ULN vs > ULN
- Sex (Female vs Male)
- ECOG (0 vs 1)

9. Interim Analysis

No interim analysis is planned.

10. Data Screening and Acceptance

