10.2 Data Handling and Electronic Transfer of Data

Amgen's Clinical Data Management (CDM) department will provide all data to be used in the planned analyses. This protocol will use the RAVE database. In addition, blood and/or tumor tissue samples for **CCI** [REDACTED], HSV antibody serostatus samples, and swab samples collected from lesions suspected to be herpetic in origin, will be processed and analyzed by a vendor of Amgen. Analysis results of these samples will be transferred to Amgen CDM on a regular basis as per a Data Transfer Plan (DTP) and will be stored on the CDM server.

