11.7.2 Detectable Talimogene Laherparepvec DNA per qPCR in Suspicious Lesions

The rate of detectable talimogene laherparepvec DNA per qPCR in suspicious lesions is defined as the number of cases of detectable talimogene laherparepvec DNA per qPCR from swabs collected from lesions that are suspected to be herpetic in origin divided by all swabs collected from these lesions. This rate will be calculated based on the Reactive Swab Analysis Set.

The subject incidence will be reported for positive qPCR for talimogene laherparepvec DNA detection in any swab of a lesion suspected to be herpetic in origin. The analysis will be based on the Reactive Swab Analysis Set. A detailed listing of qPCR results for subjects having a positive qPCR testing will be provided. In addition, a listing for all subjects in the Reactive Swab Analysis Set will be provided with reported treatment-emergent adverse events (including preferred term, verbatim term, start and end dates, duration, grade, seriousness, and relationship to IP), and qPCR result.

11.7.3 Reporting of Suspected or Known Unintended Exposure to Talimogene Laherparepvec and Herpetic Illness in Close Contacts and Healthcare Providers

Potential or known unintended exposure to talimogene laherparepvec, and any related suspected signs or symptoms in a subject's close physical contact, household member, caregiver, or healthcare provider will be reported. If consent of close contact or

healthcare provider is provided, the exposed individual may be asked to have a swab taken to evaluate for the presence of talimogene laherparepvec in suspicious lesions. The positive qPCR for talimogene laherparepvec DNA detection from suspicious lesions will be reported. These individual cases in secondary contacts will be reported with separate ID numbers to distinguish them from subjects' data. More details will be provided in a program-level SSAP for unintended exposure to talimogene laherparepvec.

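### SAP 11.7.2 counts a swab with no valid qPCR result as if it were negative, so any such swab at the primary snapshot can lower the reported herpetic-lesion rate and cannot raise it

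*Protocol*

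**What the plan says.** SAP 11.7.2 gives two summaries of qPCR findings in lesions suspected to be herpetic.

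- **Swab level.** The numerator is the number of detections; it is "divided by all swabs collected from these lesions". Nothing readable limits the denominator to swabs with a result.
- **Subject level.** "The subject incidence will be reported for positive qPCR for talimogene laherparepvec DNA detection in any swab" of a suspected lesion.

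Both use the Reactive Swab Analysis Set. SAP Section 7 defines it as enrolled, dosed subjects who "have at least one swab sample collected from lesions that are suspected to be herpetic" in origin. Having a result is not a condition of membership.

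On timing, Protocol 10.3.2 states: "The clinical study report (CSR) will be written based on the results of the primary analysis". That analysis falls when every subject has had the opportunity for 12 months of treatment. Protocol 3.5.2 puts the end of the study at 24 months after last enrolment or later. SAP Section 1 says: "The scope of this plan includes the primary analysis that is planned".

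On availability, Protocol 7.5 says that swab qPCR results "will not be provided unless requested by the investigator or the subject", and then: "Results may not be available until the end of the study". SAP 10.2 lists the herpetic-lesion swabs among the samples that a vendor analyses, with results sent to the sponsor's data management group regularly under a Data Transfer Plan.

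**The concern.** A positivity rate normally has tested specimens in its denominator. With collected specimens there instead, a swab with no valid result has the same arithmetic effect as a confirmed negative, and a reader of the table cannot tell the two apart.

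The direction matters. Protocol 10.1.1.2 names symptomatic herpetic lesions positive for the study virus as a safety endpoint, and the product is a replicating virus. A formula that can understate detection but cannot overstate it errs on the less cautious side. Swabbing also continues through safety and long-term follow-up (Protocol Table 2 and Section 7.2.4), so some swabs may be taken shortly before the primary snapshot.

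The subject-level summary has a parallel weakness. If it is expressed per subject in the Reactive Swab Analysis Set, someone whose only swab has no valid result is counted as not positive.

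**Working it through.** The plan states no expected number of swabs, no positivity rate and no share without a result, so there is no figure to reproduce. The check is algebra, with assumed values for illustration.

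**Notation.** N = swabs collected; T = swabs with a valid result at the cut-off; X = positives among T; u = (N - T)/N; p = X/T.

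**Step 1: the SAP rate.** X/N = (X/T) × (T/N) = p(1-u). This is an identity and needs no assumption.

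**Step 2: direction.** If the remaining N - T swabs were resolved, they would add Y positives, with Y between 0 and N - T. The complete rate would be (X + Y)/N, which is never below X/N. The SAP rate is therefore a lower bound on the complete rate, whatever the reason for missing results.

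**Step 3: size.** If missing results are unrelated to positivity, p estimates the complete rate, and the SAP rate understates it by the factor (1-u). The values of p and u below are assumptions.

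| u | SAP rate, p = 20% | SAP rate, p = 5% |
|---|---|---|
| 0% | 20% | 5% |
| 10% | 18% | 4.5% |
| 25% | 15% | 3.75% |
| 50% | 10% | 2.5% |

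With valid results as the denominator, the rate stays at 20% or 5% in every row.

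**Step 4: an example in counts.** Suppose 20 swabs are collected, 15 have a result and 3 are positive.

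- SAP rate: 3/20 = 15%.
- Rate among swabs with a result: 3/15 = 20%.
- Upper bound, if all 5 unresolved swabs were positive: (3 + 5)/20 = 40%.

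The SAP would print 15%, the bottom of a possible range of 15% to 40%, without showing that 5 swabs had no result.

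**Step 5: timing.** Measured from last enrolment, the gap between the primary analysis and the earliest end of study is 24 - 12 = about 12 months. Results that arrived only at the end of the study would miss the primary report. The documents do not establish that this will happen.

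**The case against.** The strongest reply is that the plan gives no evidence that any swab will lack a result.

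- A reader might infer from Protocol 7.5 that swabs stay untested until the end of the study, so that the primary report will understate the rate. The documents do not support that. The sentence follows a statement that results are not handed to the investigator or subject unless requested, because they are not expected in time to benefit the subject or alter treatment. It is conditional, and it does not say that the sponsor lacks results at the primary analysis.
- SAP 10.2 has results arriving regularly, and SAP 10.1 has inconsistent data resolved before database lock.
- Protocol 10.3.3 has the study report amended at the final analysis, so a shortfall from pending results could be temporary.
- SAP 11.7.2 also requires a listing of every subject in the set with the qPCR result, from which missing results might be seen.
- SAP 10.3, on missing data, is partly blacked out and may hold a handling rule.
- A rate among tested swabs is not assumption-free. If the more suspicious lesions were tested first, it would overstate positivity.

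Most of this stands, and it limits the point to a conditional one. It does not remove it. Regular transfer does not require that testing be complete before the snapshot. Invalid swabs would dilute the rate even if testing were prompt, and a later amendment would not remove them. A listing does not correct the summary table. If a blacked-out rule excludes swabs without results, it needs reconciling with the explicit denominator in 11.7.2. The last objection is met by printing the counts beside the rate.

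**Conclusion.** The point holds in conditional form. As worded, SAP 11.7.2 treats every swab without a valid result as negative, so such swabs can lower the reported rate but cannot raise it. Relative to the rate among swabs with a result, the reduction is exactly the share u. Reading it as the understatement of the true rate also assumes that missing results are unrelated to positivity.

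The value of u is unknown. At u = 0 nothing changes; given the regular transfers, a small u is plausible but not assured. The documents do not show that the primary report will be biased, only that its formula has no protection if results are incomplete. The summary is descriptive, so no test, error rate or sample size is affected. This is a minor improvement to a safety table.

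**What to change.** In SAP 11.7.2:

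1. Define the denominator as swabs with a valid qPCR result at the data cut-off.
2. Beside the rate, report the numbers of swabs collected, tested and without a valid result (pending, untested or invalid), and give positives over all collected, labelled as a lower bound.
3. In the subject incidence, show subjects whose only swabs lack a valid result as unknown, separately from those with a negative result.
4. Optionally, require that swabs taken before the cut-off be tested before the primary snapshot.

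Items 1 to 3 cost SAP wording and a few table rows; item 4 needs agreement with the testing vendor. If every swab has a valid result, the reported rate is unchanged. The downside is that the tested-only rate may be slightly higher and assumes that missing results are unrelated to positivity, which is why the counts and the lower bound should appear with it.
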